4.2 Secondary endpoints

4.2.1 Objectives:

The secondary objective of this trial is to assess the effects of tvCVS on cognition in people with mild/moderate PDD.

4.2.2 Endpoints:

The secondary endpoint will be the change in the Montreal Cognitive Assessment (MoCA) between the baseline and end of treatment visit (Day 84) after 12 weeks of treatment. 3 different versions of the MoCA (8.1, 8.2, and 8.3) will be used to avoid learning effects, and the ordering of the version for a given participant will be randomized. The MoCA is a rapid screening instrument for detecting cognitive dysfunction and dementia in patients with neurologic disorders including PD.

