4.3 Exploratory Endpoints

4.3.1 Objectives:

This study will also seek to further assess the effects of tvCVS on cognition and other symptoms in people with mild/moderate PDD.

4.3.2 Endpoints:

The exploratory endpoints will evaluate changes in the following between the baseline and end of treatment visit (Day 84) after 12 weeks of treatment, unless otherwise noted:

- The Zarit Burden Interview of Caregivers (ZBI) – a measure of caregiving burden completed by caregivers
- The Patient Global Impression of Improvement (PGI-I) - a patient reported outcome assessment for how much the patient's illness has improved or worsened relative to a baseline state at the beginning of the intervention. * *This version will require input from the study partner and will provide a single consensus score between the study participant and study partner.*
- The Neuropsychiatric Inventory - Questionnaire (NPI-Q) – a brief questionnaire completed by caregivers to evaluate behavioral disturbances in dementia patients – *to be completed by the study partner*
- The Modified Schwab and England Activities of Daily Living Scale (S & E)⁴⁵ - clinical outcome assessment of an individual's ability to function in activities of daily living

Treatment adherence and TNM™ Device usability/satisfaction will also be assessed.

Optional Sub-study:

For those that consent to this optional sub-study: A customized cognitive battery (CCB) which will assess the following functions (alternate versions to be used at each study visit):

- Memory
 - Hopkins Verbal Learning Test-Revised (total learning)
 - Hopkins Verbal Learning Test-Revised (delayed recall)
 - Hopkins Verbal Learning Test-Revised (recognition discrimination)
- Visuospatial
 - Neuropsychological Assessment Battery - Visual Discrimination
- Language
 - Delis-Kaplan Executive Function System - Semantic Fluency
- Attention
 - Neuropsychological Assessment Battery – Digits Forward
 - Hopkins Verbal Learning Test-Revised (Trial 1)
- Processing speed
 - Oral Symbol Digit Modality
- Executive Function

Clinician version – not for patient use

- Delis-Kaplan Executive Function System - Semantic Fluency Switching
- Neuropsychological Assessment Battery – Digits Backward

5 Study design:

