Screening steps: The screening activities should be performed per the schedule of events (SOE) noted in the appendix, and the rater assessments in the order noted below. If at any time study staff recognizes that the recruit does not meet the inclusion and exclusion criteria for the study, they will inform the individual being screened and will note the reason

SHARPEN, V3.0 -- CONFIDENTIAL

Clinician version – not for patient use

for screen failure in the study documentation.

- Mini-Mental State Examination (MMSE)
- Intake of medical history and concomitant medications
- Ear exam- *The purpose of the exam (by otoscope) is to ensure that there are no contraindications to placing the device earpieces into the ear canals such as signs of inflammation, drainage, perforation of tympanic membrane, or excessive cerumen build up. Additionally, visual inspection for obvious structural abnormalities of the ear structure and ear canal should be included. As delegated by the PI, medical professionals who hold licenses/credentials, and have appropriate training and experience may conduct the ear exam.*
- Columbia Suicide Severity Rating Scale (C-SSRS) - questionnaire regarding suicidal thoughts
- Urinalysis- this does not need to be performed at the screening visit if there are normal range values documented in the medical record within 6 months of the screening visit.
- Blood draw for screening labs - B12, TSH, CMP, and CBC w/differential may be required. These labs do not need to be performed at the screening visit if there are normal range values documented in the medical record within 6 months of the screening visit.
- Review of Inclusion and Exclusion Criteria
- Review of the general study schedule and timeline, with assessment scheduling.

Baseline Visit- day 0: The baseline activities should be performed per the SOE in the appendix maximizing the time between administration of the MoCA (to be completed first) and the Customized Cognitive Battery (alternate versions to be used at all study visits). Assessments followed by (SP) should be completed by the Study Partner only.

- Confirmation of timing of last dopamine replacement therapy (DRT) dose
- Montreal Cognitive Assessment (MoCA) v8.1 (on-state) ⁺*Of note, if the participant has completed v8.1 in their standard clinical course within 5 weeks of this administration, they should perform v8.2 at this visit, then v8.1 at the interim visit.*

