- MDS-UPDRS III - clinician-scored motor exam ⁺*Of note, the collection of MDS-UPDRS Part III data should occur in the on-state. The timing of the administration of the MDS-UPDRS Part III from dose should be recorded and kept consistent at each administration of the assessment for that participant.*
- MDS- UPDRS I –patient and caregiver in equal proportion
- MDS-UPDRS II– patient and caregiver in equal proportion
- PGI-S – should be completed with input from study participant and study partner in equal proportion
- PGI-S response documentation: study staff should ask the study participant and study partner to give at least three reasons for their score and answers will be recorded and will be provided to the study participant and study partner at future administrations of the PGI-I.
- S&E
- NPI-Q *(SP)*
- ZBI *(SP)*
- Ear Exam
- Concomitant medication and adverse event review

SHARPEN, V3.0 -- CONFIDENTIAL

Clinician version – not for patient use

Customized Cognitive Battery (CCB) Form 1 — *optional substudy* *** *The best practice is to collect this data at the baseline visit, however, if participant is unable to complete the CCB at the baseline visit, he/she may complete the CCB at the Early Treatment Period Visit 1 - day 3 visit as an alternative. The CCB must be collected at a single study visit and at the study center. Data collection of the CCB should not occur in Off-state. Tests should be administered in the following order:*

- HVLT-R (Trials 1-3)
- NAB Digits Forward
- NAB Digits Backward
- NAB Visual Discrimination
- Oral SDMT
- HVLT-R (Trial 4 and Recognition)
- D-KEFS Category Fluency (skip Condition 1-Letter Fluency for this study)
- D-KEFS Fluency Switching
- Review of inclusion/exclusion criteria
- Device dispensation and training
- First device administration with confirmation of understanding

The participant should be fitted, and the device adjusted as necessary with the ear pad selection documented. Participants should confirm that they find wearing the unpowered device to be comfortable enough to proceed with the study treatment prior to device dispensation. If they do not, the reason for screen failure should be noted in the study documentation.

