Device dispensation will occur only after all scheduled assessments and activities have been completed. The participant and study partner will be trained on how to use and care for the Device. The participant (with the assistance of the study partner as appropriate) should complete the first treatment administration at the study site to demonstrate to study staff an understanding of how to set-up, use, and clean the study Device. The participant will then take the study Device home, treat once more for the day, and continue with twice daily treatments for the duration of the treatment period.

Treatment Period: The 12 weeks (~84 days) following the pre-treatment baseline period constitute the treatment period. Participants will self-administer treatments twice daily with at least an hour in between treatment sessions, for the full treatment period up until the scheduled end of treatment visit. Treatment adherence will be recorded by the Device.

Phone contact (Day 1, +/- 1 day)

The first day (Day 1) after Device allocation, the study staff should contact the participant/study partner to confirm that treatments have been administered, that there are no questions or concerns about the Device and to review concomitant medications and potential adverse events.

Early Treatment Period Visit 1 - day 3 (+/- 3 days): *This in-clinic visit may be completed virtually at the participant and study partner's request if the customized cognitive battery does not need to be collected.* The participant and study partner should return to the clinic with the study device. The study participant (with the assistance of the study partner as

SHARPEN, V3.0 -- CONFIDENTIAL

Clinician version – not for patient use

appropriate) should complete a treatment administration at the study site to demonstrate to study staff an understanding of how to use the study Device. If participants and their study partners do not meet the criteria specified in the Treatment Administration Verification Form, the participant and study partner will be re-trained on how to use and care for the Device. The participant will then take the study Device home, treat once more for the day, and continue with twice daily treatments for the duration of the treatment period.

CCB (if not collected at the Baseline day 0 visit)- *Data collection of the CCB should not occur in Off-state. Tests should be administered in the following order:*

- HVLT-R (Trials 1-3)
- NAB Digits Forward
- NAB Digits Backward

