- MDS-UPDRS III - clinician-scored motor exam *+Of note, the collection of MDS-UPDRS Part III data should occur in the on-state. The timing of the administration of the MDS-UPDRS Part III from dose should be recorded and kept consistent at each administration of the assessment for that participant.*
- MDS- UPDRS I - patient and caregiver in equal proportion
- MDS-UPDRS II - patient and caregiver in equal proportion
- NPI-Q *(SP)*
- ZBI *(SP)*
- S&E
- Ear Exam
- Concomitant medication and adverse event review

Phone contacts: (Days 56, and 70 +/- 3 day)

The study staff should continue phone calls scheduled every 2 weeks to review concomitant medications, potential adverse events, potential issues impacting Device treatment adherence and any other issues with the study participant (and study partner, as appropriate).

End of Treatment Visit or Early Termination Visit: (Day 84 +/- 5 days)

The visit activities should be performed per the SOE in the appendix maximizing the time between administration of the MoCA (to be completed first) and the Customized Cognitive Battery. Assessments followed by (SP) should be completed by the study partner only.

- Confirmation of timing of last DRT dose
- MoCA v8.3 (on-state)
- MDS-UPDRS III - clinician-scored motor exam *+Of note, the collection of MDS-UPDRS Part III data should occur in the on-state. The timing of the administration of the MDS-UPDRS Part III from dose should be recorded and kept consistent at each administration of the assessment for that participant.*
- MDS- UPDRS I - patient and caregiver in equal proportion
- MDS-UPDRS II - patient and caregiver in equal proportion
- PGI-S/PGI-I
- NPI-Q *(SP)*
- ZBI *(SP)*
- S&E
- Device Useability Questionnaires (Study Participant and Study Partner)
- Ear Exam
- Customized Cognitive Battery (Form 2) *-optional sub study. The best practice is to collect this data in the way it was collected at baseline. For instance, if a participant completed the CCB at the Baseline Visit – day 0 they should complete the CCB at the end of treatment visit. If the first CCB was collected at the Early Treatment Period Visit 1 - day 3, the best practice would be to have them return for a separate visit within 5 days of the end of treatment visit, while continuing to treat with the study device. The CCB must be collected at a single study visit. Data collection of the CCB should not occur in Off-state. Tests should be administered in the following order:*

- HVLT-R (Trials 1-3)

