3. TREATMENT

The study is single arm with all study participants receiving time-varying caloric vestibular stimulation treatments.

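### In the optional cognitive battery sub-study, form order is fixed (Form 1, then Form 2), so the trial's own data cannot separate a difference between forms from 12-week change

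*Protocol*

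**What the plan says.** The CCB is an optional, exploratory sub-study with ten measures in six domains (Protocol 4.3.2). It is given twice.

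- **Baseline (Protocol 5.1.1, Day 0):** the entry reads "Customized Cognitive Battery (CCB) Form 1". A note under the same bullet lets the first battery move to the Day 3 visit.
- **Day 3 (Protocol 5.1.1):** the entry reads "CCB (if not collected at the Baseline day 0 visit"), and it names no form.
- **End of treatment (Protocol 5.1.1, Day 84):** the entry reads "Customized Cognitive Battery (Form 2").
- **General rule on versions:** Protocol 4.3.2 has "alternate versions to be used at each study visit", and the baseline paragraph of 5.1.1 has "Customized Cognitive Battery (alternate versions to be used at all study visits"). Both require different versions at different visits. Neither says that the order differs between participants.
- **MoCA, for contrast (Protocol 4.2.2):** "the ordering of the version for a given participant will be randomized". No such statement is made for the CCB.
- **Comparison:** "The exploratory endpoints will evaluate changes in the following between the baseline and end of treatment visit (Day 84"), in a trial of which SAP section 3 says "The study is single arm with all study participants receiving time-varying caloric vestibular stimulation treatments".
- **Analysis:** SAP 6.5 makes the Wilcoxon signed-rank test the default for paired comparisons. SAP 6.6.3 defers the CCB to a supplemental SAP, which is not among the documents.

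**The concern.** Alternate forms limit the learning of specific items. If everyone takes them in the same order, though, any difference in difficulty between the forms falls wholly on the change score. A concurrent control arm tested in the same order would carry the same form effect, and the effect would cancel from the comparison. This trial has no such arm.

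What is at stake is the purpose that SAP 6.6.3 gives for the exploratory endpoints, namely to help choose outcome measures for later trials. A form difference need not be the same for every subtest. A subtest with an easier Form 2 could look responsive and be carried forward. One with a harder Form 2 could look unresponsive, or worse, and be dropped.

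**Working it through.** The documents give no power, sample-size or form-equivalence figure for the CCB, so there is no figure of the plan to reproduce. The check covers identifiability first, then size over an assumed range.

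**1. Identifiability.** Write the expected score as μ + τT + φF, with T = 0 at baseline and 1 at end of treatment, and F = 0 for Form 1 and 1 for Form 2. Here τ is the true 12-week change and φ is the form difference.

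- *Fixed order.* The only rows (1, T, F) are (1,0,0) and (1,1,1). The rank is 2 for 3 parameters, and expected change = τ + φ. The two terms cannot be separated.
- *Balanced order.* The rows (1,0,1) and (1,1,0) are added, and the rank is 3. Participants taking Form 1 then Form 2 have expected change τ + φ. Those taking Form 2 then Form 1 have τ − φ. The average of the two group means is τ, and half their difference is φ.

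**2. Size if the order stays fixed.** Inputs:

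- Test: exact two-sided Wilcoxon signed-rank at 5%. This is the SAP 6.5 default and is *assumed* for the CCB.
- Within-person change: normal with SD 1 and no true change (assumed).
- Form difference d: 0 to 0.75 SD of change (assumed, because the documents give none).
- n: 12 is the whole treated sample (Protocol 10.1). Because the sub-study is optional, 8 and 6 are shown as well.

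Simulated share of studies with a false finding of change (the bias equals d throughout):

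| d (SD of change) | n = 12 | n = 8 | n = 6 |
|---|---|---|---|
| 0 | 4% | 4% | 3% |
| 0.25 | 11% | 8% | 5% |
| 0.5 | 32% | 19% | 11% |
| 0.75 | 61% | 39% | 21% |

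These are rounded, and repeat runs differ by about one percentage point. At n = 6 the smallest attainable two-sided p value is 2/2⁶ = 0.031, which explains the 3% at d = 0. A harder Form 2 gives the same rates in the direction of worsening.

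**3. After balancing, n = 12, six per order.** The estimate is (mean change in order A + mean change in order B)/2. Its standard error is √[(s²/4)(1/n_A + 1/n_B)], where s² is the pooled within-order variance, on n_A + n_B − 2 = 10 degrees of freedom. A plain paired analysis would have 11.

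| d | False positives: plain Wilcoxon | False positives: order modelled | Power at true change 0.75 SD: plain Wilcoxon | Power: order modelled |
|---|---|---|---|---|
| 0 | 4% | 5% | 61% | 65% |
| 0.5 | 2% | 5% | 51% | 65% |
| 0.75 | 1% | 5% | 39% | 65% |

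Both approaches are unbiased once order is balanced. A Wilcoxon test that ignores order treats the form difference as noise. Its false-positive rate falls below 5% only because power is lost. Modelling order avoids that loss.

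**4. Unequal order groups.** With 5 and 3 participants the standard error is ½√(1/5 + 1/3) = 0.365 SD, against 1/√8 = 0.354 SD for eight participants split evenly. Imbalance costs little, provided that both orders occur.

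**The case against.** **A reader might infer that no later analysis could rescue the CCB.** The documents do not support that. The confounding is complete only within the trial's own data. Published equating or form-specific norms could correct a form difference, and the supplemental SAP, which cannot be read here, might use them. What stands is that neither document mentions either.

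**A reader might take the n = 12 rates as the expected error.** They are not. Participation is optional, anyone without a Day 0 or Day 3 battery is outside the sub-study, and the Wilcoxon test is not specified for the CCB. The form difference is wholly assumed. The forms may be equivalent, and then there is no bias.

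**A reader might infer that every first battery is Form 1.** For Day 0 the text says so. For Day 3 it is an inference from the fallback note under the Form 1 bullet.

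**Materiality is limited.** The CCB does not enter the primary endpoints, the MoCA endpoint or the go/no-go criteria in Protocol 10.1 and SAP section 4. SAP 6.6.3 makes no multiplicity adjustment, so its p values are exploratory in any case. In an uncontrolled arm, 12-week change also contains residual practice, expectation and disease course. Balancing form order would not make the change attributable to the device. All of this stands. It limits the importance of the point without removing it, since balancing takes out one source of bias that can differ by subtest, at almost no cost.

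**Conclusion.** The point holds as a cheap improvement to an optional exploratory sub-study (severity: nice to have). The fixed order is in the text, and the aliasing of form with time follows from it without any assumption. The size of the bias is unknown: it equals the form difference, which may be zero, and the false-positive rates in the working depend on the assumed differences, sub-study size and test. The documents do not support reading this as evidence that the two forms differ, or as a threat to the trial's safety, feasibility or go/no-go conclusions.

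**What to change.** **Protocol 5.1.1 (Day 0, Day 3 and Day 84).** Assign form order among sub-study participants from a pre-prepared balanced list: half take Form 1 then Form 2, and half Form 2 then Form 1. Name the form in the Day 3 entry, and record the form used at each administration.

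**Supplemental SAP.** Estimate and test change as the average of the two order groups' mean changes, with order in the model. Do not use a plain Wilcoxon test that ignores order.

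**If batteries have already been given in the fixed order.** Specify form-equated or form-normed scores where they exist, and report the limitation for the remaining subtests.

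**Cost.** A few lines of text and a one-page list. Sites must track the form, one degree of freedom is spent on order, and in a very small sub-study care is needed that both orders are represented.

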5.2 Injury/Illness-Related Schedule Deviations

Additional protocol approved timing deviation can be considered for enrolled participants due to illness or injury. Participants meeting these requirements may be afforded additional time windows for in-person study visits of up to 10 days. If the injury or illness prohibits the participant from coming to the clinic during the 10-day window, but the participant is able to complete some assessments virtually via video call or phone call, data should be collected using this format with a note to file detailing the reasons for the virtual data collection.

5.3 Justification for Treatment Protocol

The results from the single-site RCT provide evidence to support the safety and effectiveness of TNM™ Device treatments for managing the symptoms associated with PD, experienced by those that have PDD. TNM™ Device treatments in this study utilized the same time-varying waveform and BID schedule as was used in a pivotal study that demonstrated TNM™ is a safe and effective prophylactic for episodic migraine. The study described herein will utilize the same active treatment waveform and BID treatment regimen as were used in these previous studies.

In this study, participants will treat for 12 weeks (84 days) rather than 8 weeks (56 days), as was the case for the single-site RCT. The selection of a longer treatment interval was based on the finding that the treatment response, including measures of relevance to PDD, did not reach an asymptote during the 8 weeks of treatment. These results suggest that additional gains may be obtained with longer treatment intervals. Notably, 12-week treatment intervals were shown to be safe for the indication of episodic migraine, and there has been no evidence from a small crossover study in PD that treatment intervals of 12-16 weeks of treatments increases the risk of device-related AEs relative to 8 weeks. The treatment interval in this study will be limited to 12 weeks to minimize confounding variables that may arise with participants changing concomitant medications.

5.4 End of Study Definition

Participants will continue to be enrolled in the study until at least 12 participants have been dispensed a study Device. The study will end when all study participants have completed their end

SHARPEN, V3.0 -- CONFIDENTIAL

Clinician version – not for patient use

of treatment (or early termination/withdrawal) visit or safety data support early termination of the study.

6 Study population

6.1 Inclusion Criteria

Inclusion Criteria: Each participant must have a pre-treatment history that, when initially screened by a principal investigator or designee, documents that she/he meets all elements of the following:

1. Adults, age 50 years of older, diagnosed with Clinically Established or Clinically Probable Parkinson's disease according to the MDS Clinical Diagnostic Criteria².
2. Participants with a clinical diagnosis of probable PDD (criteria defined in Emre et al., 2007)² according to procedures defined in Dubois et al., 2007³ (allowing for diagnosis of PD defined in Step 1 to be according to MDS Clinical Diagnostic criteria instead of the Queen Square Brain Bank Criteria).
3. Participants must be able and willing to consent to participate in the study and comply with all study requirements. If the participant is unable to consent due to limited capacity, a Legally Authorized Representative (LAR) must consent. **Capacity for consent must be assessed by a licensed clinician with experience with Parkinson's disease dementia and documented in the participant's file.*
4. Participants and investigators must expect that the participant will be able to remain on a stable regimen of concomitant therapies used for the management of PD and not to introduce new medications used to treat PD (motor or non-motor symptoms) during the study.
5. The principal investigator, or designee, must have confidence in the participant's ability to reliably use the TNM™ device, and to understand and complete the assessments (provided in English only) within a given on-state.
6. Participant must have a study partner (defined as someone who sees the participant for more than three hours a day, 5x per week) that is willing to consent and participate in the trial.

